6.2. STUDY SCHEMA FOR WAVE 3 MODIFICATION

6.3. STUDY SUMMARY

Title	Cause or effect? Untangling the relationship with amyloid and tau deposits to cognitive decline and Alzheimer's disease in the Dallas Lifespan Brain Study		
Protocol Number	Version 6		
Phase	Phase II		
Methodology	Open label		
Study Duration	5/1/2019 - 6/30/2022		
Study Center(s)	Single-center		
Objectives	We will conduct tau PET scans on up to 125 adults using the radiopharmaceutical AV-1451. This will allow us to determine tau deposition across adults of different ages and assess the relationship of current tau burden to cognitive function and amyloid deposition collected over the previous 10-year interval.		
Number of Subjects	Up to 125		
Diagnosis and Main Inclusion Criteria	Eight- to ten-year follow-up Dallas Lifespan Brain Study participants who were cognitively normal at the time of enrollment from 2008 to 2014.		
Study Product(s), Dose, Route, Regimen	[¹⁸ F]AV-1451 (7-(6-[F-18]fluoropyridin-3-yl)-5H-pyrido[4,3- b]indole) for Injection, a single intravenous (IV) bolus administration of up to a target dose of 370 MBq (10 mCi)		
Duration of administration	Single dose		
Reference therapy	Not applicable		
Statistical Methodology	Tau deposition will be examined via estimating the mean standardized uptake value ratio (SUVr) of [¹⁸ F]AV-1451 in six temporal brain regions of interest in both the left and right hemispheres. Linear mixed-model analysis will use the Tau SUVr values to examine relationships with changes in other Alzheimer's Disease pathology and changes in decline of cognitive function in brain changes associated with typical aging.		

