study eight years earlier. This population of subjects is critical to study because pathology for Alzheimer's disease starts long before clinically observable effects develop. The timing of tau development relative to amyloid is not well understood. The Wave 3 data will provide us the ability to relate tau aggregation in Wave 3 to magnitude of amyloid deposition both during Wave 3 and across the previous 8 - 10 years. We can also connect tau deposition in Wave 3 to present cognitive function and magnitude of decline over 8 - 10 years.

While [¹⁸F]AV-1451 was not available and no tau scanning was done for Wave 1 in the DLBS, we were able to conduct 60 [¹⁸F]AV-1451 PET scans in DLBS on 60 Wave 2 participants as part of a clinical trial by Avid Radiopharmaceuticals. During Wave 3 (the focus of the present protocol), we propose to manufacture [¹⁸F]AV-1451 via the UTSW Cyclotron and Radiochemistry Program. We will administer one dose to up to 125 participants in Wave 3. This portion of the study is important because it will allow us to assess longitudinal changes in [¹⁸F]AV-1451 in the 60 previously tested Wave 2 participants, and its relationship to growth in amyloid and decline in cognition. Secondly, we can see whether it increases more rapidly as a function of age. Finally, it will allow us to add to the information on [¹⁸F]AV-1451's safety profile. These data, in combination with DLBS behavioral data and MRI scanning and amyloid imaging, will provide a comprehensive picture of the aging mind over a period of years, allowing us a window into maintenance of cognitive health and, for some subjects, transition towards dementia.

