6.10. STATISTICAL CONSIDERATIONS

6.10.1. Study Design/Study Endpoints

This is a single-center study that uses two types of designs. First, the Wave 3 data will be analyzed separately and utilizes a cross-sectional design with age as a primary continuous variable, as well as multiple aspects of brain structure, brain function, cognitive performance, and amyloid deposition used as additional predictors of different types of cognitive function (memory, speed of processing, executive function). Then, in a second series of analyses that integrate data from Wave 1, Wave 2, and Wave 3, a retrospective-longitudinal design will be used to assess the relationship of present tau deposition to change in multiple aspects of brain structure, brain function, cognitive performance, and amyloid across time. Tau imaging agent administration is open-label, and imaging of participants will end when all eligible participants are scanned, all remaining participants have been contacted but are unable to be reached or unwilling to participate, or in the event that new safety data becomes available that indicates the study should be terminated. Study endpoints described in sections 6.5.4 and 6.5.5 are repeated below.

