6.10.1.2. Secondary Endpoints

Tau deposition will be estimated from Wave 3 data by the SUVr of [¹⁸F]AV-1451 in temporal regions (both left and right) of interest: (1) inferior temporal gyrus, (2) middle temporal gyrus, (3) superior temporal gyrus, (4) entorhinal cortex, (5) parahippocampal gyrus, and (6) fusiform gyrus. Amyloid accumulation will be measured as the SUVr value averaged across eight cortical regions: dorsal lateral prefrontal cortex, orbitofrontal cortex, lateral parietal cortex, posterior cingulate cortex, anterior cingulate cortex, precuneus, lateral temporal cortex, and occipital lobe. Both measures of tau and amyloid will be used as continuous measures rather than positive and negative dichotomy. In addition, there were 60 participants in Wave 2 who received tau imaging four years earlier. Change in tau deposition will be estimated for all returning participants who were among those that received tau imaging in both Waves 2 and 3. We also note that for all endpoints described below, we will analyze the data exclusively from Wave 3 in cross-sectional analyses, and then will also calculate change in all of these endpoints from Wave 1 to 3, and then retrospectively relate tau levels to changes in these endpoints.

- **6.10.1.2.1.** Hippocampal volume and regional cortical thickness will be estimated using FreeSurfer (ver. 5.3), with surface parcellation manually edited, when necessary, by our team of experts.
- **6.10.1.2.2.** Estimates of white matter integrity will be collected using diffusion tensor measures. For functional measures, BOLD signal from contrasts of interest using selected ROI's will be created using our

subsequent memory task and semantic judgment task and their relationship to tau deposition will be assessed. In addition, we will also use resting state data to look at how tau effects functional brain connectivity.

- **6.10.1.2.3.** Joint effects of tau and amyloid will be examined by including them as an interaction term in a linear mixed-model analysis.
- 6.10.1.2.4. Cognitive decline will be assessed using the following constructs: processing speed, episodic memory, working memory, and executive function. Scores on these constructs will be averaged across relevant DLBS tasks and standardized based on performance at the beginning of this longitudinal study (Wave 1).

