6.10.3. Data Analyses

For all analyses, testing the primary and secondary objectives of this study, our measures of interest will be measured continuously and entered into linear regression or linear mixed-models analyses as appropriate. For each objective, as we have noted earlier, we will first analyze the data cross-sectionally within Wave 3 to determine whether tau SUVr is related with our dependent variables. A test-wise alpha of 0.05 will determine finding significance regarding research hypotheses, and post hoc analyses will be corrected for family-wise error using the multi-stage Holm-Bonferroni method (Holm, 1979). Then we will model changes from Waves 1 - 3 in endpoints and their relationship to tau at Wave 3.

- **6.10.3.1.** Our primary objective, to determine the time course of tau deposition with age, will be first assessed by computing a linear regression between the AV-1451 SUVr in each of our temporal regions of interest with participant age. Next, we will determine whether this relationship is better fit by a quadratic, exponential, or growth model. We predict that tau accumulation will accelerate in old age, thus supporting a non-linear rate of deposition.
- **6.10.3.2.** A linear mixed-model analysis will be used to relate our continuous SUVr measure of amyloid deposition with the SUVr for tau deposition in each of our temporal ROIs. An amyloid SUVr x time of testing interaction term will be used to predict changes in tau SUVr. We predict that increased amyloid burden will be associated with accelerated tau deposition.
- **6.10.3.3.** To determine differences in cognitive, structural, and functional decline between those with and without tau and amyloid pathology, we will perform multiple linear mixed-model analyses. All variables of interest will be included as continuous measures. Tau SUVr x time and amyloid SUVr x time interaction terms will be entered in these models to predict how amyloid and tau pathology predicts longitudinal changes in our cognitive, structural, and functional measure of interest. In line with recent research, we predict tau burden in particular to be strongly associated with more rapid structural and cognitive decline.

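### Tau at Wave 3 is related to decline already completed over Waves 1–3, so the tau–decline models show association only; the Wave 2 tau scans permit a lagged analysis that is not planned

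*Combined protocol and SAP*

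**What the plan says.** The study title in 6.3 begins "Cause or effect? Untangling the relationship with amyloid and tau deposits to cognitive decline". Section 6.10.1 describes the longitudinal part openly: "a retrospective-longitudinal design will be used to assess the relationship of present tau deposition to change" in brain structure, brain function, cognition and amyloid. Section 6.10.1.2 adds that the analysis will calculate change in each endpoint from Wave 1 to Wave 3 and "then retrospectively relate tau levels to changes in these endpoints". Section 6.10.3 confirms the timing: "Then we will model changes from Waves 1 - 3 in endpoints and their relationship to tau at Wave 3". In 6.10.3.3, tau SUVr by time and amyloid SUVr by time terms are entered "to predict how amyloid and tau pathology predicts longitudinal changes in our cognitive, structural, and functional measure of interest". Section 6.10.3.5 does the same with a tau by amyloid by time term.

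On the available scans, 6.4.4 states that "no tau scanning was done for Wave 1", and 6.10.1.2 that "there were 60 participants in Wave 2 who received tau imaging four years earlier". The plan gives the Wave 2 scans three uses:

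- change in tau from Wave 2 to Wave 3 in people scanned twice (6.10.1.2);
- amyloid as a predictor of change in tau (6.10.3.2);
- the relation of tau change to amyloid growth and cognitive decline, mentioned in the rationale (6.4.4) but not carried into 6.10.3.

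None of these relates the Wave 2 tau level to decline after Wave 2.

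**The concern.** In the tau–decline models the explanatory variable is measured after the outcome interval has closed. Section 6.10.1.1 reinforces this: cognition, MRI and amyloid PET come from visits before the tau scan. A positive tau by time coefficient is then expected if tau drove the decline, if neurodegeneration came first and tau followed, or if both had a common source. More participants would make the association more precise without changing this.

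At stake is how the results may be read. The title asks about direction, and objective 6.5.2.3 speaks of a detrimental effect of tau on change. A reader who meets a significant tau by time term described as predictive may take it as evidence that tau came first. Meanwhile the one set of tau scans that precedes some of the decline is not used for that purpose.

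**Working it through.** **The plan's own figure.** Section 6.10.2 gives power 0.93 for r = 0.30 with 125 subjects. Section 6.10.3 gives alpha 0.05 per test; sidedness is not stated. By Fisher's z, power = Φ(atanh(r)·√(n − 3) − 1.96), with atanh(0.30) = 0.3095.

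- n = 125: 0.3095 × 11.045 − 1.96 = 1.459, so power is 0.928. The two-sided test reproduces 0.93; a one-sided test gives 0.96 to 0.97. This is power to detect an association and says nothing about order.

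**Can the planned test separate the two directions?** An illustrative simulation with 3,000 runs per case, standardised variables and an assumed path strength of 0.35:

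- *Decline first.* Wave 2 tau depends on Wave 1–2 decline (0.35). Wave 3 tau = 0.8 × Wave 2 tau + 0.35 × Wave 2–3 decline + 0.5 × noise. Tau has no effect on later decline. The implied correlation of Wave 3 tau with total decline is (0.8 × 0.35 + 0.35)/√(1.0125 × 2) = 0.44.
- *Tau first.* Decline in each interval depends on tau at its start (0.35), and tau correlates 0.8 from wave to wave. The implied correlation is (0.35 × 0.64 + 0.35 × 0.8)/√2.196 = 0.34.

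| Test | Decline first | Tau first |
|---|---|---|
| Wave 3 tau against Wave 1–3 decline, n = 125 | over 99% significant | 98% significant |
| Wave 2 tau against Wave 2–3 decline, n = 60 | 5% | 79% |

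The planned comparison is significant, with the same sign, under both mechanisms. The lagged one differs. The 5% depends on an assumption that decline in one interval is unrelated to decline in the next.

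**What happens when decline persists?** A second simulation used decline driving tau (0.35), no tau effect, n = 60, measurement-error SD half the between-person SD, and adjustment for the Wave 2 level only. The lagged test then rejected falsely in about 9%, 14% and 20% of runs when successive declines correlated 0.3, 0.5 and 0.7. Wave 2 tau can simply mark decline already under way, so Wave 1–2 change belongs in the model. Because observed change contains error, that adjustment reduces the problem without removing it.

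**Precision of a lagged analysis.** Simple correlation of 0.30, two-sided 0.05. The number of the 60 who return at Wave 3 is not given, so the smaller numbers are assumptions.

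- n = 60: 0.3095 × 7.550 − 1.96 = 0.377, power 0.65. The 95% interval is tanh(0.3095 ± 1.96/7.550), about 0.05 to 0.51.
- n = 50: power 0.56.
- n = 40: 0.3095 × 6.083 − 1.96 = −0.077, power 0.47.
- n = 30: power 0.36.
- For 80% power: (1.960 + 0.842)²/0.3095² + 3, about 85 people.

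With four adjustment covariates and an assumed partial correlation of 0.30, n − 3 becomes n − 7. Power is then Φ(0.3095 × √53 − 1.96) = 0.62 at n = 60 and Φ(0.3095 × √33 − 1.96) = 0.43 at n = 40.

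**The case against.** The strongest reply is that the plan does not claim what it is faulted for. It calls the design retrospective, and 6.4.4 calls the study observational. The primary objective (6.5.1.1) and objective 6.5.2.1 ask about relationships. The stated hypothesis is itself about association: "we predict tau burden in particular to be strongly associated with more rapid structural and cognitive decline". Predict is ordinary regression vocabulary. Most of this stands. The timing is disclosed, and on wording the fault is confined to how the time-interaction terms are described in 6.10.3.3 and 6.10.3.5. Disclosure, however, does not supply the missing ordered analysis.

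Three stronger readings are tempting, and the documents do not support them.

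- A reader might infer that the title question cannot be answered at all. Amyloid was imaged in earlier waves, so past amyloid accumulation against later tau (6.5.2.2) is in temporal order. Section 6.10.3.2 can be too, provided earlier-wave amyloid enters; the text does not say which wave is used.
- A reader might infer that the Wave 2 tau scans serve only to estimate tau change. Section 6.10.3.2 and the rationale in 6.4.4 give them further uses. Relating two changes over the same interval still does not establish which came first, so the gap is specifically the lagged tau-to-decline analysis.
- A reader might infer that a lagged model would settle the matter. The persistence check above shows otherwise: temporal order supports a causal reading but does not prove it.

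It is also fair that at most 60 people give low power, and that the addition changes neither the primary endpoint nor conduct. That limits how much weight the analysis can bear. It is not a reason to omit it when the Wave 2 scans already exist and Wave 3 repeats the Wave 2 measures (Figure 1).

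**Conclusion.** The point holds for the tau–decline part of the title question and no further. The models in 6.10.3.3 to 6.10.3.5 show association between Wave 3 tau and prior decline, and cannot distinguish tau driving decline from decline preceding tau. The stated power of 0.93 is correct for association with 125 people.

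A lagged analysis of the Wave 2 scans is feasible and would add some information on order. Its power is about 0.65 at best for a simple correlation of 0.30, somewhat less after adjustment, and about 0.47 if 40 return. This rests on the protocol's own effect size carrying over to a lagged relation, and on assumed return numbers. The simulations are illustrative: their path strengths, error size and correlations between successive declines are assumptions. This is a worthwhile low-cost improvement to a secondary analysis, not a defect in the primary endpoint.

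**What to change.** 1. **Wording.** In 6.10.3.3 and 6.10.3.5, describe results for Wave 3 tau by time, alone or with amyloid, as associations with prior decline.

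2. **One supportive lagged analysis.** In the up to 60 people with Wave 2 tau, regress the Wave 3 outcome (cognition, hippocampal volume, cortical thickness) on Wave 2 tau SUVr, adjusting for the Wave 2 level of that outcome, Wave 1–2 change, age and Wave 2 amyloid. This needs Wave 3 cognition or MRI but no second tau scan. Name one tau summary in advance, since six regions in two hemispheres give 12. A mixed-model counterpart over Waves 1–3 would have a separate Wave 2–3 slope and Wave 2 tau by slope terms for both intervals. It must not also carry the Wave 2 outcome as a covariate, because that score is already an outcome in the model.

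3. **Optional reverse model.** Relate Wave 1–2 decline to Wave 2–3 tau change in people scanned twice. Its sample may be smaller than in item 2 because it needs both scans, so it should have its own precision statement.

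4. **Reporting.** Give estimates with confidence intervals beside the retrospective models, state the number analysed, and label the analyses supportive.

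These should be fixed before the data are examined. Section 6.5.3.1 allows follow-up analyses prompted by findings, and a lagged model added that way would carry less weight. The cost is a few extra models and some redrafting, with no additional scans or visits. The downside is low precision, so a null lagged result should not be read as evidence against an effect of tau.

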6.10.2. Sample Size and Accrual

To fulfill the primary objective of this research project, we intend to conduct tau PET imaging with up to 125 adults that were typically-aging at the start of this study. Scanning will take place over the span of the next 2 years with an anticipated accrual rate of approximately 7 subjects per month. This accrual rate was based on our experience imaging participants in the previous wave of data collection.

Statistical power was computed using G*Power (ver 3.1) assuming successful collection of tau data for the full 125 subjects and using default G*Power parameters unless otherwise specified. The secondary objectives of this study (Sections 6.5.2.1 - 6.5.2.4) are assumed to involve linear relationships between variables for the purpose of this power analysis. With this sample size, we have an estimated power of 0.93 to detect linear relationships that are medium-sized (effect size: r = 0.30). This robust power level will allow for strong confidence in our findings, computation of more precise 95% confidence intervals on effect sizes, and more fine-grained post hoc analysis.

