6.5.2. Secondary Objectives

- **6.5.2.1.** To assess the relationship of tau burden to hippocampal volume and cortical thickness and their contributions to predicting decline in memory and other cognitive functions.
- **6.5.2.2.** To determine whether rate of amyloid accumulation over the past 8 10-year interval predicts tau deposition.
- **6.5.2.3.** To examine the detrimental effect of tau deposits, as well as the joint effect of tau and amyloid, on changes in brain activity and cognitive function.
- **6.5.2.4.** To examine differences in cognitive, structural, and functional decline between those with and without amyloid and tau pathology.

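### The 0.93 power in section 6.10.2 does not carry over to the tau-change term in 6.10.3.2, which rests on at most 60 people with paired tau scans

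*Combined protocol and SAP*

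**What the plan says.** Section 6.10.2 has one power calculation. Its sample is stated as "assuming successful collection of tau data for the full 125 subjects", and its scope as "The secondary objectives of this study (Sections 6.5.2.1 - 6.5.2.4) are assumed to involve linear relationships between variables". The result is "With this sample size, we have an estimated power of 0.93 to detect linear relationships that are medium-sized (effect size: r = 0.30". The next sentence calls this power robust and draws strong confidence in the findings from it, without qualification.

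Section 6.10.3 then lists the models, introduced with "For all analyses, testing the primary and secondary objectives of this study". Item 6.10.3.2 relates amyloid to tau in each temporal region and adds: "An amyloid SUVr x time of testing interaction term will be used to predict changes in tau SUVr". It also predicts a direction, namely that higher amyloid burden goes with faster tau deposition.

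On the tau data, 6.10.1.2 separates level from change. For level: "Tau deposition will be estimated from Wave 3 data by the SUVr". For change: "Change in tau deposition will be estimated for all returning participants who were among those that received tau imaging in both Waves" 2 and 3. The same section gives 60 people scanned at Wave 2. Section 6.4.4 says that Wave 1 had no tau scans and that up to 125 people receive one dose each at Wave 3.

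**The concern.** A term that predicts change in tau needs at least two tau scans in the same person. At most 60 people can have them, fewer than half of the 125 behind the power figure. Section 6.10.2 gives no separate figure for this subset, and 6.10.3.2 is the listed analysis that has tau as outcome and amyloid as predictor. A reader will therefore carry 0.93 over to it.

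What is at stake is how a null result is read. If the interaction in 6.10.3.2 is not significant, 0.93 suggests that a medium-sized association would have been missed only 7% of the time. The result could then pass for good evidence that amyloid does not speed tau deposition, when the design could well have missed such an effect.

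**Working it through.** **Inputs from the protocol**
- n = 125, r = 0.30, stated power 0.93 (6.10.2); test-wise alpha 0.05 (6.10.3).
- Sidedness is not stated. Two-sided is inferred because it reproduces 0.93, whereas one-sided gives 0.96.
- Tau scans: none at Wave 1, 60 at Wave 2, one per person at Wave 3 (6.4.4, 6.10.1.2). Section 6.4.3.1 mentions a third tau scan, but on 6.4.1 and 6.4.4 nobody can have more than two.

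**Assumptions not in the protocol**
- r = 0.30 also applies to the association of amyloid with tau change.
- The within-person correlation of tau, ρ, lies between 0.3 and 0.9.
- The return rate of the 60 to Wave 3 is varied below.

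**Step 1: reproduce the stated figure.** With Fisher's z, power ≈ Φ(atanh(r)·√(n − 3) − 1.960), and atanh(0.30) = 0.3095.
- n = 125: 0.3095 × √122 = 3.419; 3.419 − 1.960 = 1.459; Φ = 0.928.
- The exact bivariate-normal calculation gives 0.930, so the plan's 0.93 is confirmed.

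**Step 2: the same test with 60 pairs.**
- n = 60: 0.3095 × √57 = 2.337; 2.337 − 1.960 = 0.377; Φ = 0.647.
- Exact: 0.654.

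**Step 3: credit the Wave 3-only scans.** Section 6.10.3.2 specifies a mixed model, which can also use the other 125 − 60 = 65 people. Take a random-intercept model with n pairs and m Wave 3-only people. Relative to pairs alone, the information on amyloid × time is multiplied by 1 / [1 − ((1 − ρ)/2) · m/(n + m)], where m/(n + m) = 65/125 = 0.52.
- ρ = 0.9: 1/(1 − 0.05 × 0.52) = 1.027. Power ≈ Φ(0.3095 × √(57 × 1.027) − 1.960) = 0.658.
- ρ = 0.3: 1/(1 − 0.35 × 0.52) = 1.222. Power ≈ Φ(0.3095 × √(57 × 1.222) − 1.960) = 0.734.
- Generalised least squares with random amyloid values and a t reference on 58 degrees of freedom gives 0.665 to 0.739 over the same range.

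The two methods together give about 0.66 to 0.74.

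**Step 4: incomplete return.** No return rate is given for the 60. Section 6.4.1 has two sets of Wave 1-to-2 counts: 183/296 = 62% in the text and 338/464 = 73% in Figure 1. Applied to the 60, these give 60 × 0.618 ≈ 37 and 60 × 0.728 ≈ 44 pairs.

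| Data for the test of r = 0.30 | Power, two-sided 0.05 |
|---|---|
| 125 people, one linear relationship with Wave 3 tau | 0.93 |
| 60 pairs + 65 Wave 3-only, mixed model | 0.66–0.74 |
| 60 pairs alone | 0.65 |
| 44 pairs alone | 0.52 |
| 37 pairs alone | 0.45 |

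**Step 5: detectable effect.** From 60 pairs, r at 80% power ≈ tanh((1.960 + 0.842)/√57) = tanh(0.371) = 0.355 (exact 0.352). For 0.93 power the exact figure is 0.42.

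**The case against.** The strongest reply is that 6.10.2 says nothing false. It ties its figure to objectives 6.5.2.1 to 6.5.2.4, and none of these names change in tau as an outcome. Objective 6.5.2.2 reads "To determine whether rate of amyloid accumulation over the past" 8 to 10 years predicts tau deposition, and 6.10.1.2 estimates deposition from Wave 3 data. The limit to people scanned twice is also disclosed, in the section just before the power statement. Both facts are right. So a reader who infers that objective 6.5.2.2 as worded, or the secondary objectives in general, lack the stated power goes further than the documents allow: analyses with Wave 3 tau as outcome or predictor can draw on up to 125 people. The reply still leaves a gap. Section 6.10.3 presents the tau-change term as a test of the objectives, with a directional prediction, and disclosing the 60 is not the same as stating power for them.

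A second reply is that 0.65 comes from a correlation in the pairs and is not the planned mixed model. That is fair, and it is why the range up to 0.74 is given. The mixed-model figure depends on ρ, which the documents do not supply, but no value in the range examined brings it near 0.93.

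A third is that a mixed model could also use the Wave 2 scans of people who do not return. With 48 pairs (an assumed 80% return) and 77 Wave 3-only people, adding the 12 Wave 2-only people moves power from 0.57–0.66 to about 0.58–0.71. The pairs-alone figures for incomplete return are therefore pessimistic for the planned model, but the conclusion stands.

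Finally, the 60 is historical and the 125 is a dose allocation, so neither can be raised. This bears on the remedy and leaves the point itself untouched.

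**Conclusion.** Wrong as written, and a minor wording correction. The arithmetic behind 0.93 is sound; the fault is its scope. It holds for a single simple linear relationship, r = 0.30, two-sided 0.05, with Wave 3 tau in all 125 people. It does not hold for the amyloid-by-time term on tau change in 6.10.3.2. There the chance of missing r = 0.30 is about 26 to 35% with full return of the 60, against an implied 7%. From pairs alone it is about 48 to 55% if only 44 to 37 return.

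These sizes rest on carrying r = 0.30 over to change, on ρ between 0.3 and 0.9, and on the Wave 1-to-2 return rates as a guide to Wave 3. That at most 60 people supply within-person change rests on no assumption.

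Two further inferences should be resisted. One is that the study is too small: nothing here calls for more participants. The other is that 0.93 is confirmed for every analysis that uses Wave 3 tau. It was not computed for the three-way interaction in 6.10.3.5 or for the non-linear age fits in 6.10.3.1.

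**What to change.** In 6.10.2, limit the 0.93 and the sentence on robust power to a single simple linear relationship with Wave 3 tau in the full 125. Say that the figure was not computed for interaction terms (such as 6.10.3.5) or for the non-linear fits in 6.10.3.1.

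Then add that the tau-change term in 6.10.3.2 rests on at most 60 paired scans. For r = 0.30 its power is about 0.65 from the pairs alone at full return, somewhat higher in the mixed model depending on the within-person correlation, and lower with incomplete return. The detectable r at 80% power is about 0.35 from 60 pairs.

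Sample size, procedures and models do not change. The only cost is that the stated power for one planned analysis becomes less favourable.
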